5.3. Safety Variables

Safety variables include incidence of TEAEs (grade 3 or 4; for phase 1 only), treatment-emergent SAEs, and treatment-emergent AESIs (as defined in Section [10.1.3](#)).

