9.2.3.2. Adverse Event Monitoring

Treatment-emergent serious adverse events (as defined in Section 10.2.1) and treatment-emergent AESIs (as defined in Section 10.2.3) will be recorded. In phase 1, TEAEs (grade 3 or 4) will also be recorded.

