4.6. Safety Variables

4.6.1. Adverse Events and Serious Adverse Events

Treatment-emergent adverse events (AEs) (grade 3 or 4; for phase 1 only), treatment-emergent serious adverse events (SAEs) and treatment-emergent adverse events of special interest (AESIs) will be collected according to the Schedule of Events (Appendix 10.1 and Appendix 10.2). All adverse events are to be coded using the Medical Dictionary for Regulatory Activities (MedDRA).

Treatment-emergent adverse events are defined as those that are not present at baseline or represent the exacerbation of a pre-existing condition.

Infusion-related reactions are defined as any relevant adverse event that occurs during the infusion or up to day 4.

Hypersensitivity reactions are defined as any relevant adverse event that occurs during the infusion or up to study day 29.

The severity of adverse events (including test findings classified as adverse events) will be graded using the current version of the NCI-CTCAE v5.0 (Division of Cancer Treatment and Diagnosis [DCTD], 2020).

Treatment-emergent AEs, treatment-emergent SAEs, or treatment-emergent AESIs not listed in the NCI-CTCAE will be graded according to the scale in [Table 8](#).

Table 8: NCI-CTCAE Severity Grading System for Adverse Events

Grade	Severity	Description
1	Mild	Asymptomatic or mild symptoms; clinical or diagnostic observations only; intervention not indicated
2	Moderate	Minimal, local, or noninvasive intervention indicated; limiting age appropriate instrumental activities of daily living (ADL)*
3	Severe	Severe or medically significant but not immediately life threatening; hospitalization or prolongation of hospitalization indicated; disabling; limiting self-care ADL†
4	Life-threatening	Life threatening consequences; urgent intervention indicated
5	Death	Death related to adverse events

*Instrumental ADL refers to preparing meals, shopping for groceries or clothes, using the telephone, managing money, etc.

† Self-care ADL refers to bathing, dressing, and undressing, feeding self, using the toilet, taking medications, and not bedridden.

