5.7. Analysis of Safety Data

The analysis of safety data will be performed for cohort 1 in combined phases 1, 2 and 3, phase 2 cohorts 1A, 2 and 3, separately in the FAS population.

In this study, only targeted treatment-emergent adverse events will be recorded:

- All phases: Treatment-emergent adverse events of special interest (AESIs)
 - Grade ≥ 2 hypersensitivity
 - Grade ≥ 2 infusion-related reactions
- All phases: Treatment-emergent serious adverse events (SAEs)
- All phases: TEAEs (Grade 3 or Grade 4 only)

The safety analysis will be based on the reported SAEs and AESIs and other safety information (clinical laboratory evaluations and vital signs).

Thresholds for Potential Clinically Significant Values (PCSV) in laboratory variables and vital signs are defined in Section [10.3](#).

The summary of safety results will be presented for each treatment group.

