5.7.1. Adverse Events

Summaries that include frequencies and proportions of patients reporting AEs will include the PTs and the SOCs.

An overview of adverse events will be provided by treatment group and for combined dose groups of R10933+R10987, including:

- Total number of TEAEs, SAEs, Total number of AESIs, Serious AESIs, Grade 3 or 4 TEAEs, as well as
- The number and percentage of patients with
 - any TEAE, any SAE, any AESI, any serious AESI, any grade 3 or grade 4 TEAE, any fatal TEAEs, any TEAEs leading to withdrawal from the study, any TEAEs leading to study infusion discontinuation, and any TEAEs leading to study infusion interruption.

Summaries of SAEs and AESIs by treatment group and for combined R10933+R10987 doses will include number (n) and percentage (%) of patients with at least :

- Treatment-emergent AE by SOC and PT
- Treatment-emergent AE by SOC and PT and CTCAE grade

- Treatment-emergent AE related to study treatment by SOC and PT
- Treatment-emergent SAE by SOC and PT
- Treatment-emergent AESIs presented by SOC and PT
- Treatment-emergent grade 3 or 4 AEs presented by SOC and PT

Counts will be provided according to treatment group for each PT within each SOC. Percentages will be calculated using the number of patients from the FAS in each treatment group.

Primary SOCs will be sorted according to decreasing order of frequency in combined treatment group. Within each primary SOC, PTs will be sorted by decreasing frequency in combined treatment group.

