5.9. Analysis of Immunogenicity Data

5.9.1. Analysis of ADA Data

Immunogenicity variables will be summarized using descriptive statistics.

Immunogenicity will be characterized by the ADA responses and titers observed in subjects in the ADA analysis set. ADA response categories and titer categories are defined as follows:

ADA response categories:

- ADA Negative, defined as ADA negative response in the ADA assay at all time points, regardless of any missing samples.
- Pre-existing immunoreactivity, defined as either an ADA positive response in the ADA assay at baseline with all post first dose ADA results negative, OR a positive response

at baseline with all post first dose ADA responses less than 9-fold over baseline titer levels.

- Treatment-emergent response, defined as an ADA positive response in the ADA assay post first dose when baseline results are negative or missing. The treatment-emergent responses will be further characterized as Persistent, Indeterminate or Transient.
 - Persistent Response (only applicable to phase 1) – Treatment-emergent ADA positive response with two or more consecutive ADA positive sampling time points, separated by at least 16-week period (based on nominal sampling time), with no ADA negative samples in between, regardless of any missing samples.
 - Indeterminate Response –Treatment-emergent ADA positive response with only the last collected sample positive in the ADA assay, regardless of any missing samples.
 - Transient Response –Treatment-emergent ADA positive response that is not considered persistent or indeterminate, regardless of any missing samples.
- Treatment-boosted response, defined as a positive response in the ADA assay post first dose that is greater than or equal to 9-fold over baseline titer levels, when baseline results are positive.

Titer categories (Maximum titer values)

- Low (titer <1,000)
- Moderate (1,000 ≤ titer ≤ 10,000)
- High (titer >10,000)

The following analysis will be provided:

- Number (n) and percent (%) of ADA-negative subjects (pre-existing immunoreactivity or negative in the ADA assays at all time points) by treatment arms
- Number (n) and percent (%) of treatment-emergent ADA positive subjects by treatment arms and ADA titer categories
 - Number (n) and percent (%) of persistent treatment-emergent ADA positive subjects
 - Number (n) and percent (%) of indeterminate treatment-emergent ADA positive subjects

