10.2.1. Footnotes for Schedule of Events (Phase 2)

1. Every effort should be made to perform all screening and baseline activities on the same day. Randomization within the IRT system and administration of study drug should occur on the same day (day 1). All samples will be collected before study drug administration at baseline visit except post-infusion PK samples.
2. For a given day, the visit may occur in clinic, as a home-based visit (defined as visits by home health care staff, at mobile units, and/or testing centers), or by phone. All samples will be collected as indicated whether the patient is hospitalized or has been discharged.
3. Patients must provide separate consent to collect blood samples as part of the optional PGx sub-study. Blood sample for RNA must be collected pre-dose on day 1. Blood sample for DNA should be collected at the screening/baseline visit but may be collected at any visit.
4. Refer to protocol Section 9.2.1.2 for diagnostic test requirements during screening.
5. Pregnancy testing will be performed locally in women of childbearing potential (WOCBP) only. Negative pregnancy test must be confirmed prior to study drug administration. Serum or urine pregnancy test are both acceptable. Refer to protocol Section 9.2.3.4 for more information on pregnancy testing and contraceptive measures.
6. Medical history should include collecting onset of pneumonia symptoms.
7. Clinical and oxygen status will be collected 3 times during the screening/baseline visit period: prior to randomization, just prior to dosing, and post-dose. Clinical and oxygen status will be collected and recorded in the eCRF as described in protocol Section 9.2.5.2.
8. Vital signs (including temperature, blood pressure, heart rate, and SpO₂) will be collected pre-dose and post-dose, as described in protocol Section 9.2.3.1.
9. Only treatment-emergent SAEs and AESIs will be recorded in the eCRF.
10. Patients discharged from the hospital may receive phone follow-up for treatment-emergent SAEs, treatment-emergent AESIs, and/or targeted concomitant medications as indicated in protocol Table 2 (post-discharge phone follow-up). These visits may occur in addition to any in-person visit listed for the given day. Phone visits will have a window of ± 1 day.
11. Medications will be reviewed and recorded. Only the targeted medications listed in protocol Section 9.2.3.3 will be recorded in the eCRF.

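### SAP 5.7 says grade 3/4 TEAEs are recorded in all phases, but outside phase 1 only SAEs and AESIs are, so two pooled cohort 1 overview rows mix collection rules and understate incidence

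*SAP*

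**What the plan says.** On which phases record grade 3/4 TEAEs, the documents disagree:

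- SAP 5.7: "All phases: TEAEs (Grade 3 or Grade 4 only").
- SAP 4.6.1: "Treatment-emergent adverse events (AEs) (grade 3 or 4; for phase 1 only").
- SAP 10.2.1, footnote 9 to the phase 2/3 schedule: "Only treatment-emergent SAEs and AESIs will be recorded in the eCRF".
- Protocol 5.3: "Safety variables include incidence of TEAEs (grade 3 or 4; for phase 1 only").
- Protocol 9.2.3.2: "In phase 1, TEAEs (grade 3 or 4) will also be recorded".

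The protocol synopsis, protocol 10.1.1 and footnote 9 in protocol 9.1.2.1 take the same position as protocol 5.3.

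On the tables, SAP 5.7 analyses cohort 1 with phases 1, 2 and 3 combined, and cohorts 1A, 2 and 3 separately, all in the FAS. SAP 5.7.1 plans an overview with rows for any TEAE and any grade 3 or 4 TEAE, followed by tables by SOC and PT. Its denominator rule is: "Percentages will be calculated using the number of patients from the FAS in each treatment group". No phase 1 denominator and no footnote is given for the grade 3/4 rows. Protocol 11.4.10.1 carries the same rows and the same denominator.

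**The concern.** A phase 1 patient with a non-serious grade 3 event that is not an AESI is counted. A phase 2 or 3 patient with the same event is not, because the eCRF does not record it. Both sit in the same denominator. The pooled cohort 1 percentage for these two rows is therefore neither a rate of all grade 3/4 events nor a rate of SAEs and AESIs alone.

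SAP 5.7 makes this harder to see, since a reader who relies on it will take the row as complete in every patient. In cohorts 1A, 2 and 3, which have no phase 1 patients, the same line implies a completeness that does not exist for any patient. At stake is the absolute incidence of severe events as reported, and the ability to see an arm difference in the non-serious part.

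**Working it through.** **Is the SAP 5.7 line a deliberate change?** SAP 1.2.4 states that nothing is modified from the statistical section of protocol amendment 7. In the current protocol, section 11.4.10 defines the targeted events by pointing to 10.1.1, which says phase 1 only. The protocol's amendment history (Amendment 2) also introduced this collection for phase 1 only. The line is best read as an error.

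**Counts (SAP 2.3).** Check against the stated total: 60 + 609 + 629 + 164 + 35 + 755 = 2252, which agrees. Cohort 1 pooled: 60 + 629 + 755 = 1444 randomized. Phase 1 share: 60/1444 = 4.2%. Remainder: 1444 − 60 = 1384. With 1:1:1 allocation this is about 20 phase 1 patients among about 481 per arm, and 40 among about 963 for the combined doses. The size of the FAS is not given; it can only be equal or smaller.

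**Non-serious, non-AESI component alone.** The reported percentage is the phase 1 percentage × 60/1444, a factor of 1444/60 = 24.1. An assumed 10% would contribute 0.42%, and 20% would contribute 0.83%.

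**The whole grade 3/4 row.** SAEs and AESIs are recorded in all phases and are graded (SAP 4.6.1; SAP 6.3 assigns a grade even when it is missing). They therefore enter the row from all 1444 patients. Let

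- *a* = share of patients whose only grade 3/4 events are non-serious and non-AESI;
- *s* = share with a grade 3/4 SAE or AESI.

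Assume both are the same in every phase. Full capture would give *a* + *s*. The row reports [60(*a* + *s*) + 1384*s*]/1444 = *s* + 0.0416*a*. The documents give neither *a* nor *s*, so both are assumed: *a* from 5% to 30%, *s* from 5% to 25%.

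| *a* | *s* | Full capture | Reported | Understatement |
|---|---|---|---|---|
| 5% | 25% | 30% | 25.2% | 1.2-fold |
| 10% | 10% | 20% | 10.4% | 1.9-fold |
| 20% | 15% | 35% | 15.8% | 2.2-fold |
| 30% | 5% | 35% | 6.2% | 5.6-fold |

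The first and last lines are the extremes of the range. The any-TEAE row has the same structure; it was not quantified separately.

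**The case against.** The strongest reply is that SAP 5.7 goes on to base the safety analysis on reported SAEs and AESIs, and SAP 5.7.1 introduces the SOC/PT tables, including the grade 3/4 one, as summaries of SAEs and AESIs. On that reading numerator and denominator match. This stands for the SOC/PT tables. It does not cover the overview, whose two rows carry no such limit; if only SAEs and AESIs are meant there, the rows are mislabelled.

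It can also be said that protocol 3.2.1.5 and 10.2.4 mention grade 3/4 collection without a phase limit. Neither says all phases, and neither displaces the explicit restrictions elsewhere. SAP 1.2.5 cites a separate phase 1 SAP that is not available here, so these events may already have been tabulated for phase 1 alone. That would not correct the pooled rows.

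A reader might infer more than the documents support:

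- *That the row divides events from about 60 patients by 1444, a 24-fold understatement.* It does not: grade 3/4 SAEs and AESIs from the other 1384 patients count too. The 24-fold figure belongs to a component that no planned row reports by itself.
- *That the error favours the active arms.* Allocation is 1:1:1 in every phase, so the dilution is about equal across arms. It lowers absolute rates and shrinks differences.
- *That the safety endpoints are compromised.* Those in protocol 4.1 and 4.2 are SAEs, grade ≥2 infusion-related reactions and grade ≥2 hypersensitivity reactions, all collected in every phase.
- *That the ADA categories share the fault.* SAP 5.9.1 already marks "Persistent Response (only applicable to phase 1"). Any difficulty there is one of classification and is not part of this point.

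**Conclusion.** The phase label in SAP 5.7 is wrong and conflicts with the SAP's own section 4.6.1 and phase 2/3 footnote as well as with the protocol. Followed as written, it leaves two descriptive overview rows in pooled cohort 1 with mixed capture and percentages that are too low. For the grade 3/4 row the understatement is about 1.2- to 5.6-fold. That range rests on the assumed event rates, on equal rates across phases, and on randomized rather than FAS counts. In cohorts 1A, 2 and 3 the same rows can hold only SAEs and AESIs.

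This should be fixed, but it is not critical: the SAE and AESI endpoints are unaffected and no arm is favoured. Even with the right denominator, arm comparisons of the phase 1-only events rest on about 20 patients per arm and will be weak.

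**What to change.** 1. In SAP 5.7, change the phase label on the grade 3/4 TEAE line to phase 1 only.
2. Present the full-capture rows for any TEAE and any grade 3 or 4 TEAE for phase 1 patients, with the phase 1 FAS as denominator.
3. In pooled cohort 1 and in cohorts 1A, 2 and 3, restrict these rows to SAEs and AESIs and label them so. Keep the grade, so that severity information validly collected in phases 2 and 3 is not lost.
4. Make the same change in protocol 11.4.10.1.

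The cost is wording and table shells. No new data are needed.

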5.7.1. Adverse Events

Summaries that include frequencies and proportions of patients reporting AEs will include the PTs and the SOCs.

An overview of adverse events will be provided by treatment group and for combined dose groups of R10933+R10987, including:

- Total number of TEAEs, SAEs, Total number of AESIs, Serious AESIs, Grade 3 or 4 TEAEs, as well as
- The number and percentage of patients with
 - any TEAE, any SAE, any AESI, any serious AESI, any grade 3 or grade 4 TEAE, any fatal TEAEs, any TEAEs leading to withdrawal from the study, any TEAEs leading to study infusion discontinuation, and any TEAEs leading to study infusion interruption.

Summaries of SAEs and AESIs by treatment group and for combined R10933+R10987 doses will include number (n) and percentage (%) of patients with at least :

- Treatment-emergent AE by SOC and PT
- Treatment-emergent AE by SOC and PT and CTCAE grade

- Treatment-emergent AE related to study treatment by SOC and PT
- Treatment-emergent SAE by SOC and PT
- Treatment-emergent AESIs presented by SOC and PT
- Treatment-emergent grade 3 or 4 AEs presented by SOC and PT

Counts will be provided according to treatment group for each PT within each SOC. Percentages will be calculated using the number of patients from the FAS in each treatment group.

Primary SOCs will be sorted according to decreasing order of frequency in combined treatment group. Within each primary SOC, PTs will be sorted by decreasing frequency in combined treatment group.

5.7.2. Clinical Laboratory Measurements

Laboratory test results will be summarized by baseline and change from baseline to each scheduled assessment time with descriptive statistics.

A treatment-emergent Potential Clinically Significant abnormal value (PCSV) is a laboratory value that was normal at Screening and Baseline but abnormal after treatment with study drug. See Appendix [10.3](#) for the criteria of PCSV values.

Number and percentage of patients with a potentially clinically significant value (PCSV) at any post-randomization time point will be summarized for each clinical laboratory test for all patients and separately for patients in whom the PCSV criterion was normal or missing at baseline.

Shift tables based on baseline normal/abnormal and other tabular and graphical methods may be used to present the results for laboratory tests of interest.

5.7.3. Analysis of Vital Signs

Vital signs (temperature, pulse, blood pressure, SpO₂, FiO₂, and respiration rate) will be summarized using descriptive statistics. Number and percentage of patients with a potentially clinically significant value (PCSV) at any post-randomization time point will be summarized.

5.8. Analysis of Pharmacokinetics, Pharmacodynamics and Biomarker Data

5.8.1. Analysis of Drug Concentration Data

Concentrations of REGN10933 and REGN10987 over time will be summarized by descriptive statistics for each treatment group. No formal statistical hypothesis testing will be performed.

Phase 1 (Dense Sampling)

The PK parameters to be determined after the first dose for REGN10933 and REGN10987 may include, but are not limited to:

- C_{\max}
- C_{\max}/Dose
- t_{\max}
- AUC_{last}
- AUC_{inf}
- $AUC_{\text{inf}}/\text{Dose}$
- $t_{1/2}$
- CL
- V_{ss}
- MRT

Selected PK parameters will be summarized by descriptive statistics by treatment group. All parameters will be summarized (mean, SD, %CV, range, median, and number of samples).

5.8.2. Analysis of Pharmacokinetics and Pharmacokinetics/Pharmacodynamics

At a minimum the viral-exposure response analysis will be performed.

5.9. Analysis of Immunogenicity Data

5.9.1. Analysis of ADA Data

Immunogenicity variables will be summarized using descriptive statistics.

Immunogenicity will be characterized by the ADA responses and titers observed in subjects in the ADA analysis set. ADA response categories and titer categories are defined as follows:

ADA response categories:

- ADA Negative, defined as ADA negative response in the ADA assay at all time points, regardless of any missing samples.
- Pre-existing immunoreactivity, defined as either an ADA positive response in the ADA assay at baseline with all post first dose ADA results negative, OR a positive response

at baseline with all post first dose ADA responses less than 9-fold over baseline titer levels.

- Treatment-emergent response, defined as an ADA positive response in the ADA assay post first dose when baseline results are negative or missing. The treatment-emergent responses will be further characterized as Persistent, Indeterminate or Transient.
 - Persistent Response (only applicable to phase 1) – Treatment-emergent ADA positive response with two or more consecutive ADA positive sampling time points, separated by at least 16-week period (based on nominal sampling time), with no ADA negative samples in between, regardless of any missing samples.
 - Indeterminate Response –Treatment-emergent ADA positive response with only the last collected sample positive in the ADA assay, regardless of any missing samples.
 - Transient Response –Treatment-emergent ADA positive response that is not considered persistent or indeterminate, regardless of any missing samples.
- Treatment-boosted response, defined as a positive response in the ADA assay post first dose that is greater than or equal to 9-fold over baseline titer levels, when baseline results are positive.

Titer categories (Maximum titer values)

- Low (titer <1,000)
- Moderate (1,000 ≤ titer ≤ 10,000)
- High (titer >10,000)

The following analysis will be provided:

- Number (n) and percent (%) of ADA-negative subjects (pre-existing immunoreactivity or negative in the ADA assays at all time points) by treatment arms
- Number (n) and percent (%) of treatment-emergent ADA positive subjects by treatment arms and ADA titer categories
 - Number (n) and percent (%) of persistent treatment-emergent ADA positive subjects
 - Number (n) and percent (%) of indeterminate treatment-emergent ADA positive subjects
 - Number (n) and percent (%) of transient treatment-emergent ADA positive subjects

Number (n) and percent (%) of treatment-boosted ADA positive subjects by treatment groups and ADA titer categories

- Number (n) and percent (%) of treatment-boosted ADA positive subjects by treatment arms and ADA titer categories

Listing of all ADA titer levels will be provided for subjects with pre-existing, treatment-emergent and treatment-boosted ADA response.

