2.4.1. Definition of Study Completion

For individual patients, study completion is defined as collection of vital status information on their projected EOS date. All measures will be taken to obtain vital status information on the projected EOS date, and all patients with recorded vital status information at projected EOS date will be considered study completers. The end of study is considered day 169 (for phase 1) or day 57 (for phase 2 and phase 3) (refer to Section 10 Schedule of Events).

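### ADA responders still positive at their last sample are counted as transient, because indeterminate requires that sample to be the only positive one and transient takes the remainder

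*SAP*

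**What the plan says.** SAP 5.9.1 and Protocol 11.4.12 give the same definitions.

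- **Entry.** A treatment-emergent response is "defined as an ADA positive response in the ADA assay post first dose when baseline results are negative or missing". Patients positive at baseline go to the pre-existing or treatment-boosted categories and are not part of this point.
- **Split.** "The treatment-emergent responses will be further characterized as Persistent, Indeterminate or Transient".
- **Persistent.** The definition opens "Persistent Response (only applicable to phase 1") and requires consecutive positive time points "separated by at least 16-week period (based on nominal sampling time"), with no negative sample in between.
- **Indeterminate.** A treatment-emergent "positive response with only the last collected sample positive in the ADA assay".
- **Transient.** A treatment-emergent "ADA positive response that is not considered persistent or indeterminate, regardless of any missing samples". No later negative sample is required.

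The number and percentage in each sub-category are planned outputs, and the transient row carries no phase limit. SAP 2.4.1 fixes follow-up: "The end of study is considered day 169 (for phase 1) or day 57 (for phase 2 and phase 3"). SAP 1.1 and Protocol section 11 plan the ADA analysis for cohort 1 with phases 1, 2 and 3 combined, and for phase 2 cohorts 1A, 2 and 3 separately.

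**The concern.** Most readers will take *transient* to mean that the response was seen to go away. Under these rules it does not mean that. The category also collects patients who were positive at more than one post-dose sample and still positive at the final one. *Indeterminate* looks like the natural place for a response whose duration is unknown because sampling ended, but its definition admits only patients with a single positive result.

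At stake is how one pair of rows in the immunogenicity table is read. Immunogenicity is a stated secondary objective, and Protocol 3.3.2 lists its clinical consequences among the important potential risks. A transient count that mixes cleared and uncleared responses cannot tell a reader how many responses resolved.

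**Working it through.** There is no planned figure to reproduce, so the check applies the written rules to possible sample patterns.

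**Inputs.** The definitions are those of SAP 5.9.1. Follow-up ends at day 169 in phase 1 and day 57 in phases 2 and 3 (SAP 2.4.1). The phase 2/3 ADA row in SAP 10.2 is read here as one baseline sample and two later ones, at discharge before day 29 and at day 29. The table columns are broken in the available text, so this reading is an assumption.

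**Step 1: can the persistent rule be met in phases 2 and 3?** The rule needs 16 × 7 = 112 days between positive time points, on nominal sampling times.

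- Day 1 to day 29: 28 / 7 = 4 weeks.
- Day 1 to day 57: 56 / 7 = 8 weeks.

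Both fall short of 16 weeks, even when counted from the dosing day. The long COVID sub-study continues to day 180 at some sites, but its schedule (Protocol Table 3) lists no ADA sample. In phase 1 the rule can be met: day 57 to day 169 is 112 / 7 = 16.0 weeks, and day 29 to day 169 is 140 / 7 = 20.0 weeks.

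**Step 2: classify phase 2/3 patterns, with baseline negative or missing.**

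| Earlier sample | Last scheduled sample | Class under the rules |
|---|---|---|
| − | + | indeterminate |
| + | not taken | indeterminate |
| not taken | + | indeterminate |
| + | − | transient |
| + | + | transient |

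The last two rows share a label, although one response cleared and the other did not. Rows two and five show the oddity most clearly: a patient positive at the earlier sample is indeterminate if the later sample is never taken, but becomes transient if it is taken and is also positive.

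**Step 3: sensitivity to the schedule.** With a hypothetical five post-dose samples up to day 57, all positive, the class is still transient. With day 29 as the only post-dose sample, a positive result is indeterminate. The problem therefore needs at least two positive post-dose results. Given those, it does not depend on the exact sampling days, provided sampling ends by day 57.

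**Step 4: which clause causes it?** Removing the phase 1 restriction while keeping the 16-week requirement leaves every all-positive phase 2/3 pattern unchanged. The cause is the single-positive condition in *indeterminate* combined with a residual *transient*. The same gap exists in phase 1. For illustration, a patient positive at days 29 and 57 with no later sample has a span of 28 / 7 = 4 weeks. That patient is not persistent, has two positives and so is not indeterminate, and is therefore transient.

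**Step 5: the combined cohort 1 table.** By randomized counts (SAP 1.1), cohort 1 has 60 + 629 + 755 = 1444 patients. Only the 60 phase 1 patients, 60 / 1444 = 4.2%, could be called persistent. For the other 1384 (95.8%) the persistent row is zero by construction. These are randomized counts; the ADA analysis set will be smaller.

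**The case against.** The best defence is that *transient* is defined openly as a remainder, identically in both documents, and is nowhere said to mean observed clearance. On its own terms the plan misclassifies nobody, and a table footnote would tell the reader what the row contains. It is also true that no responder is lost. Treatment-emergent positives are tabulated by arm and titer category, every titer is listed for these patients, and NAb status is reported separately. The safety and efficacy associations in SAP 5.10.2 use treatment-emergent or boosted status, maximum titer and NAb, not this split.

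That limits the consequence but does not remove the point. The row is a planned output, its ordinary meaning is resolution, and nothing in either document warns the reader otherwise.

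Three stronger readings are tempting, and the documents do not support them.

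- *That limiting persistent to phase 1 is what causes the problem.* The restriction reflects a follow-up too short to show persistence, and lifting it alone changes nothing (steps 1 and 4).
- *That the strongest responses receive the most reassuring label.* The plan grades strength by maximum titer. Two positive samples do not imply a high titer, and an indeterminate patient may have a higher one. The documents do not rank the three labels by how reassuring they are.
- *That the secondary immunogenicity endpoint is compromised.* The endpoint is ADA and NAb as such. Persistence is not an endpoint, and the analysis is descriptive.

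**Conclusion.** The point holds as a defect in two category definitions. A treatment-emergent responder with two or more positive post-dose samples including the last, who does not meet the 16-week rule, is reported as transient although the response was still present at the last sample. This applies to all such patients in phases 2 and 3 and to phase 1 patients who miss the rule.

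The impact is confined to the descriptive transient and indeterminate counts. Total treatment-emergent ADA, titer categories, NAb and efficacy results do not change. The number of affected patients cannot be derived, because the documents give neither ADA rates nor sample-level results.

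The conclusion assumes that at least two post-dose ADA samples are available for some patients and that phase 2/3 ADA sampling ends by day 57. It does not depend on reading the broken schedule tables exactly. This is a minor point, worth correcting because doing so costs so little.

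**What to change.** In SAP 5.9.1 and Protocol 11.4.12:

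1. Leave the persistent definition as it is.
2. Define **indeterminate** as treatment-emergent, not persistent, with the last collected sample positive.
3. Define **transient** as treatment-emergent, not persistent, with the last collected sample negative.
4. State that persistence cannot be assessed in phases 2 and 3. In the combined cohort 1 table, report the persistent row with a phase 1 denominator.

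The *not persistent* condition is needed in both items 2 and 3. Without it, a phase 1 patient who met the 16-week rule and was negative at the last sample would satisfy both the persistent and the transient definitions.

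SAP 1.2.4 declares no departure from the protocol's statistical section, so either both documents change together or the SAP records the difference there. The change amounts to two reworded definitions and one note, with trivial reprogramming and no new data.
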